10.3. Investigational Product Packaging and Labeling

Investigational product will be packaged by Johnson and Johnson. The investigational product will be stored in a secure area at room temperature.

Study product label will be affixed to the outer container of all investigational products. The label will contain the following information:

- Protocol Number
- Site Identification
- Treatment Code
- 24-Hour Emergency Phone Number
- Directions for Use
- For Investigational Use
- Warnings
- Net Contents
- Storage Conditions

10.4. Method of Assigning Subjects to Treatment Groups

As subjects sign a consent form, each subject will be sequentially issued a subject ID. The subject ID is an eight-digit number, beginning with the four-digit site ID “1001” and the remainder of the numerals assigned in ascending numerical order beginning with 1001, 1002, 1003, etc.

At the baseline visit, each qualified subject will be assigned a unique randomization number (e.g., 1 to 35) which determines the bandage assignment sequences. The assigned treatment will be carried out on the same wound site for Days 0 through 14. Once a randomization number has been assigned to a subject, it cannot be reassigned to another subject in that part. The assignments of the treatments and control will be based on the randomization scheme devised by the Quantitative Sciences Department at the Sponsor.

10.5. Study Product Storage and Accountability

The Investigator, or a designated study staff will ensure that investigational product is stored in a secured area under room temperature of approximately 68 °F to 77 °F (20 °C to 25 °C), in accordance with applicable regulatory requirements.

The Investigator must maintain adequate records documenting the receipt, use, loss, or other disposition of the investigational product on an investigational product accountability log. The log must identify the investigational product and account for its disposition on a subject-by-subject basis, including specific dates. The log must be signed by the individual who dispensed, and copies must be provided to the Sponsor.

At the end of the study, the Sponsor will provide instructions for the disposition of investigational product as well as any containers used for dispensation of investigational product.

10.6. Administration of the Investigational Product

All investigational products will be administered at the site by trained study staff. Study staff will apply each bandage according to the randomization schedule and protocol. Subjects will not apply products at home. All used bandages will be discarded at the study site.

10.7. Blinding and Unblinding

Due to the nature of the study, it is not feasible to reliably blind the investigational product or to conceal the identity of the treatment assignments from study subjects or all study personnel (e.g. those involved in dispensing and providing instructions on use of the assigned investigational product, reviewing subject diaries for completeness, reviewing investigational product compliance and reviewing subject-reported adverse events). Staff responsible for product accountability and dispensing will not complete any assessments or sampling. Subjects will be instructed not to disclose information about their assigned study treatments to the clinician or study staff completing any of the assessments, or to discuss any other information that may reveal the treatment assignment. While staff completing the assessments will not know the treatment assignments to each site, due to the nature of this study, it is not possible to completely blind the assessors as one site is unwounded/untreated, and the other sites may have adhesive residue generally indicating the test sites assigned to a bandage.

The randomization scheme will be used by the Johnson & Johnson Consumer's Clinical and Consumer Packaging Operations Department to generate the subject specific single disclosure envelopes. The site clinical study coordinator will receive one package containing individual subject specific disclosure envelopes indicating treatment decode for each randomization number. Identification of the treatment assignments to each site for a subject may be revealed in the event of a serious adverse event by opening the single

subject specific envelope that displays the subject's randomization number. In such an instance, the Investigator will, if circumstances and time permit, contact the Sponsor prior to breaking the code. The date and reason for such unblinding must be described on the subject's source document. Upon completion of the study, all subject specific disclosure envelopes must be returned to the study monitor who will return them to the sponsor.

Treatment assignments should only be revealed when required and only for the subject in question. The Investigator must notify the Sponsor, when circumstances and time permit, prior to unblinding of any subject. Expectedness of serious and related adverse events should be assessed using the Safety Attestation letter and/or, for marketed products, the locally approved labeling.

If there is a medical emergency and the Investigator deems it necessary to know the subject's study treatment urgently for the subject's proper medical care, the Investigator may break the treatment code immediately, and then contact the Study Director or designee as soon as possible afterward. If in the opinion of the Investigator it is necessary to break the treatment code and circumstances allow, the Investigator will first contact the Study Director or designee for consultation about breaking the study blind.

10.8. Product Quality Complaints

A Product Quality Complaint (PQC) for a non-marketed product is any written, electronic, or oral communication that alleges deficiencies related to the identity, quality, durability, reliability, or safety of a product, including its labeling, delivery system or packaging integrity. This does not include effectiveness, preference, or performance measures, which will be reviewed in aggregate at appropriate intervals.

A PQC for a marketed product is any written, electronic, or oral communication that alleges deficiencies related to the identity, quality, durability, reliability, safety, effectiveness or performance of a product after it is released for distribution.

Any PQC discovered during the initial inventory should follow the instructions provided on the receipt letter; no PQC form should be filed for issues identified when opening or unpacking a shipment. Subsequently, any observation of a PQC requires immediate notification to the study manager via a completed PQC form and telephone call. The Investigator or designee should complete, sign, and forward a copy of the PQC form to the Sponsor. Contact information will be provided.

In addition, PQC information must be noted on the investigational product accountability log or equivalent in the comments field. A Sponsor representative may assist in answering questions related to this process. To aid in the initial conversation and understanding of a PQC, the site staff may be asked to photograph the issue and send it to the Study Manager.

11. STUDY PROCEDURES

11.1. Visit 1 /Screening (3-14 days prior to V2)

Prior to their screening visit, potential subjects will be pre-screened over the telephone by the initial inclusion and exclusion criteria. Subjects who meet the pre-screening eligibility, will be given an appointment time for their screening visit. The screening visit can occur upto 14 days prior to the Baseline Visit. Subjects will be clearly instructed when to begin the wash-out period.

The following procedures will be performed at Visit 1 (Screening):

- Obtain informed consent – Study personnel will conduct the informed consent form (ICF) discussion with the subject and address any questions or concerns related to the study procedures. Subjects who agree to participate will sign the ICF before any study-related procedures are performed. Subjects will be given a copy of their signed ICF;
- Collect demographic information;
- Obtain significant medical history and prior medication history (including medication use within the last 28 days);
- Ensure that the subject meets the inclusion and none of the exclusion criteria;
- Trained study personnel will examine the subject's back to determine if the subject meets the study entrance criteria;
- Females determined to be of child-bearing potential will have a urine pregnancy test(dipstick). This test must be negative to continue in the study;
- Subjects who meet all study entrance criteria will be provided written and verbal instructions for a 3 day wash-out period [REDACTED] [REDACTED]. They will also use this body wash for the remainder of the study;
- An appointment time for the Baseline Visit (Day 0) will be provided,

11.2. Visit 2 / Baseline Visit/ Day 0

Subjects will return to the clinic following the 3 day wash-out period. The following study procedures will be performed:

- Update any changes in medical history or prior medications and non-drug therapies and confirm subject eligibility
- Assess for adverse events since last visit
- Trained study personnel will examine the subject's back again to ensure subject still meets the study entrance criteria;

Wound Care Microbiome Study
Protocol: CO-170726100607-SACT
Amendment 2: 22JAN2018

- Eligible subjects will be assigned a randomization number which will specify which test sites will be wounded and the treatment assignments for each site.
- Subjects will acclimate in the test facility for at least 15 minutes in a temperature controlled setting of 68-75°F.
- Six test sites will be identified on the back.
- 5 test sites will be wounded using a tape-stripping method as described in Section 11.8, five uniform wounds will be created by the trained study staff on the subjects back according to the randomization schedule.
- Four of the test sites will be wounded and covered with various marketed adhesive bandages (treatment groups); one test site will be wounded and un-covered (positive control) and one test site will remain intact and un-covered (negative control).
- The following assessments will completed on each test site, in the order below:
 - [REDACTED]
 - Trans Epidermal Water Loss (TEWL; tewameter): Noninvasively measures water evaporation from the skin, which is a measure of skin barrier function. These measurements will be done three times for each test site.
[REDACTED]
 - [REDACTED]
 - Diffuse Reflectance Spectroscopy (DRS): Noninvasively measures redness by oxy-, deoxy-hemoglobin, and melanin levels in the skin. Five repetitive spectra acquisition will be implemented for each test site.
 - Microbiome [REDACTED] sampling: Swabs will be used to collect bacteria [REDACTED] from the test site surface. A total of 2 swabs will be taken per test site, plus control swabs.
- Bandages will be placed on the wounds according to the randomization schedule.
- Subjects will be provided written and verbal instructions.
- Subjects will be informed of their next appointment.

- Subjects will report back to the study facility for daily bandage changes (Days 1-14) and for assessments on Days 1-7 and 14. All clinic visits will be at approximately the same time.

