11.8.1. Site Selection

Six test sites will be identified by the investigative staff and numbered from 1 to 6. The selected sites will be free from nevi or other skin conditions. Using a template and permanent marker, six (6) test areas will be marked at least 2" – 3" apart from each other

on the back on each subject. Test sites will be positioned side by side on a rectangular design so that three are made on each side of the spine. The test sites will be located paraspinally with three test sites on each side of the mid back below the shoulder blades.. Enough space will be left between the test sites so that the bandages can be placed over the wounds without an overlap. If the subject is female, the test sites will be positioned below the bra line.

The randomization schedule will detail the treatment assignments for each test site. Tape Stripping Procedure & Preparation

- The subjects will rest in a prone position (front or ventral surface downward) for the wounding procedure. Instruments used will be sterile. The Investigator or trained clinician creating the wounds as well as assisting staff will wear gloves. Test sites may be re-marked as needed.
- All test sites will be cleaned with an alcohol wipe prior to wounding. NOTE: the test site randomly assigned to be intact (unwounded) and untreated will not be wiped with alcohol.
- Superficial irritation will be created by a tape stripping method to obtain a glistening layer using 3M tape or similar ,(3M St. Paul, MN, USA) for sequential stripping of the epidermis of the test site.
- Strips may be pre-cut and placed on release paper.
- Approximately a 1 cm x 1 cm wound will be created on each of the designated test sites.
- The technician will place the tape on the test site, press it down, rub firmly within the test site marks, and remove the strip with a strong and quick stroke.
- This process will be repeated until a clear glistening layer will be visualized upon removal of the strip. The number of stripplings necessary to reach the glistening layer varies among subjects and depends upon the thickness and looseness of the subject's stratum corneum layer.
- The number of strips used per site will be recorded in the source document.

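### All six treatment assignments are fixed before wounding and the wounder is not masked, so injury severity could differ by assigned condition; releasing only the intact site first would close this route at small cost.

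*Protocol*

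**What the plan says.** Protocol 11.2 (Day 0) assigns the randomization number before acclimation, site marking and wounding: "Eligible subjects will be assigned a randomization number which will specify which test sites will be wounded and the treatment assignments for each site". Table 1 also lists randomization ahead of wounding. Section 11.2 continues: "five uniform wounds will be created by the trained study staff on the subjects back according to the randomization schedule". Section 11.8.1 says what that schedule contains, directly before the tape-stripping steps: "The randomization schedule will detail the treatment assignments for each test site".

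The stopping point for each wound is visual: "This process will be repeated until a clear glistening layer will be visualized upon removal of the strip". No fixed number of strips and no instrument target is given. The count is kept: "The number of strips used per site will be recorded in the source document". It does not appear in the SAP's covariates (4.5), model (6.3), tables (Appendix 1) or listings (Appendix 2).

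On masking, 10.7 separates roles in one direction: "Staff responsible for product accountability and dispensing will not complete any assessments or sampling". It adds that assessors will not know the assignments, while admitting that this cannot be complete. The person who makes the wounds is not mentioned.

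Only one part of the allocation is needed before stripping, namely which site is left alone: "the test site randomly assigned to be intact (unwounded) and untreated will not be wiped with alcohol". Product identity is first needed at a step that 11.2 lists after the Day 0 assessments and swabs: "Bandages will be placed on the wounds according to the randomization schedule".

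**The concern.** Five wounds per subject are meant to be the same injury, so that later differences between them reflect the covering. If the person stripping can see which wound will stay uncovered and which will be bandaged, and decides by eye when to stop, severity can come to depend on the assigned condition. Such a tendency would run in the same direction across subjects and would not average out. It would feed into the contrast between covered and uncovered wounds, which is the primary objective (Protocol 8).

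Section 10.7 gives two reasons why assessors cannot be fully masked: one site is unwounded, and bandages leave adhesive residue. Neither prevents masking among the five sites while they are being wounded. Masking is achievable at that step, but the protocol does not ask for it.

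**Working it through.** **Plan's own figure.** There is none to reproduce. Protocol 14 says the sample size is not based on power, and no SD or effect size is given. Every effect size below is an assumption.

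**Inputs from the documents.** About 35 subjects randomized for at least 30 completers (Synopsis). Each subject carries all six conditions. Tests are two-sided at 0.05 and exploratory (SAP 6.2). Change from baseline is modelled with product, baseline value and a random subject effect (SAP 6.3). By the order of steps in 11.2 and Table 1, Day 0 measurements follow wounding. This is read from the order and is not stated outright.

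**Assumptions.** Five wounded sites, n = 30, no true product effect. Site severity has SD 1 within subject, and one condition is wounded deeper by d. Severity affects the later outcome with slope b = 0.7, and the outcome has within-subject SD 1. Baseline reflects severity with reliability λ. λ = 0 stands for a baseline that carries no severity information.

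**Closed form for one contrast.**
- Residual bias after adjustment: b × d × (1 − λ).
- Standard error: sqrt(1 − b²λ) × sqrt(2/n), where sqrt(2/30) = 0.258.
- False-positive rate: Φ(z − 1.96) + Φ(−z − 1.96), with z = bias/SE.

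For d = 0.5:
- λ = 0: bias 0.7 × 0.5 = 0.35, SE 0.258, z = 1.36, rate 27.3%.
- λ = 0.6: bias 0.35 × 0.4 = 0.14, SE 0.840 × 0.258 = 0.217, z = 0.65, rate 9.9%.
- λ = 0.8: bias 0.07, SE 0.201, z = 0.35, rate 6.4%.
- λ = 0.95: bias 0.0175, SE 0.189, z = 0.09, rate 5.1%.

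**Simulation under the same assumptions** (3,000 runs; change from baseline with the baseline covariate, using within-subject contrasts among the five wounded sites):

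| Shift d | No severity information | λ = 0.6 | λ = 0.8 | λ = 0.95 |
|---|---|---|---|---|
| 0 | 4.8% | 5.2% | 5.3% | 4.8% |
| 0.3 | 13.2% | 6.3% | 5.0% | 4.6% |
| 0.5 | 27.3% | 9.8% | 6.1% | 5.5% |

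The Monte Carlo error near 5% is sqrt(0.05 × 0.95/3000) = 0.4 percentage points, so the simulated and closed-form figures agree. The simulation treats subject as fixed and leaves out the intact site. It approximates the planned mixed model and does not replicate it.

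**Reading.** If the baseline is taken after wounding, it removes most of an assignment-driven shift from the TEWL and DRS contrasts. The d = 0 row is what the fix achieves: the error rate returns to its nominal level, with sample size, alpha, visits and model unchanged.

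**Microbiome.** The documents state who analyses these endpoints (Protocol 14 and 14.2) but show no model, so no rate can be computed for the planned analysis.

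**The case against.** The strongest reply is that nothing shows the wounder sees the assignments. Section 11.2 says a number is assigned, not who reads the decode. Labels carry a treatment code (10.3), and 10.7 places the decode in subject-specific disclosure envelopes. This stands: visibility is an inference from 11.2 and 11.8.1. It does not dispose of the point, because a code that always means the same product, or sight of which wound stays uncovered, would be enough.

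Second, safeguards exist. All wounds share one visual target and are meant to be uniform, strips are counted, and the baseline covariate appears to carry severity. For TEWL and DRS this largely stands, as the working shows. The strip count, however, is used in no planned analysis. Day 0 swabs are also listed after wounding, so a post-wounding microbiome baseline exists, but no use of it as an adjustment is described. An adjustment may exist in the external partner's method, which is not shown.

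Third, the study is exploratory and unpowered. That lowers the stakes, but does not justify leaving open a bias that is easy to prevent.

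Stronger readings are tempting and should be resisted:
- A reader might infer a motive, on the view that one test bandage is the sponsor's. Product names and manufacturers are redacted, so the documents do not support this.
- A reader might infer that technicians differ in force or strip number. Section 11.8.1 attributes variation in strip number to subjects' skin; variation between subjects does not by itself bias within-subject contrasts.
- A reader might apply unadjusted error rates to TEWL and DRS, for example 12.1% or 21.3% for an outcome shift of 0.2 or 0.3 within-subject SD at n = 30. Those describe a contrast without the baseline covariate, which is not the planned analysis.

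**Conclusion.** The point holds as an avoidable gap in masking, not as a demonstrated bias. The allocation of all six sites precedes wounding, depth is ended by eye, and the wounder is not masked, although only the intact site must be known at that stage. Whether any shift would occur, and how large it would be, cannot be learned from the documents.

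The likely consequence for TEWL and DRS is small. Under the assumptions above, a 0.5 SD severity shift leaves false positives at about 5.5% to 10% with a post-wounding baseline of reliability 0.6 to 0.95, against 27% without severity information. That reassurance depends on Day 0 readings really following wounding. For the primary microbiome endpoints no comparable protection is described, and the concern is greatest there. The change is worth making because it is cheap and acts on the primary contrast.

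**What to change.** 1. In 11.2 and 11.8.1, mark the six sites first. Then release to the wounder only the number of the site that stays intact. At present the number is assigned before the sites are identified.
2. Withhold the bandage and uncovered-control assignments of the other five sites until all wounds, Day 0 assessments and swabs are complete. Then release them to the dispensing staff for bandage placement.
3. State in 10.7 that wounding staff are masked to these five assignments, including treatment codes and covered/uncovered status, until that point.
4. Add to the SAP a table of strip count by assigned condition for the five wounded sites, as a check.

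The cost is small but not zero: a second sealed release per subject, rewording of three protocol sections, one SAP table, and entry of the strip counts, which 11.8.1 places only in the source document. No extra subjects, staff, visits or measurements are needed. The change removes only assignment-driven differences among the five wounded sites. Differences in depth from chance or body position remain.

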11.3. Visits 3 -9 / Days 1-7

Subjects will be required to report to the study site at approximately the same time each visit. day for all visits. The following procedures will be completed:

- Update any changes in medical history or concomitant medications and non-drug therapies.
- Assess for adverse events since last visit.
- Subjects will acclimate in the test facility for at least 15 minutes in a temperature controlled setting of 68-75°F.
- Bandages will be removed prior to assessments.
- Wound assessments outlined at visit 2 will also be completed at these visits in the order listed below:
 - [REDACTED]
 - Trans Epidermal Water Loss (TEWL; tewameter): Noninvasively measures water evaporation from the skin, which is a measure of skin barrier function. These measurements will be done three times for each test site.
 - [REDACTED]
 - [REDACTED]
 - Diffuse Reflectance Spectroscopy (DRS): Noninvasively measures redness by oxy-, deoxy-hemoglobin, and melanin levels of the skin. Five repetitive spectra acquisition will be implemented for each test site.
 - Microbiome [REDACTED] sampling: Swabs will be used to collect bacteria [REDACTED] from the test site surface. A total of 2 swabs will be taken per site, plus control swabs, per time point.
 - A new bandage will be applied to each site as applicable.

- Subjects will be provided written and verbal instruction.
- Subjects will be informed of their next appointment.

